1.0 Project Summary/Abstract

The term *patient context* refers to the myriad *contextual factors* in patients' lives that complicate the application of research evidence to patient care.¹ For instance, the inability of a patient to afford a medication for a particular condition is a contextual factor. Contextual factors can be addressed when correctly identified. Substituting a low cost generic for a high cost brand name medication may enable a patient to afford a medication. Addressing contextual factors in a care plan is termed *contextualizing care*.² Conversely, the failure to address a contextual factor when it is feasible to do so is a *contextual error*, because it results in an inappropriate plan of care.³ In sum, contextual errors are medical errors caused by inattention to patient context. They are common and linked to both diminished health care outcomes⁴ and an increase in health care costs related to overuse and misuse of medical services.⁵ These findings were determined using a validated method for coding audio recorded data called Content Coding for Contextualization of Care ("4C")⁶ collected during the encounters by both real patients, and by unannounced standardized patients (USPs) employing checklists.⁷

Preventing contextual errors requires heightening clinician responsiveness to clues that there are contextual factors during the clinical encounter, in real time.^{8, 9} These clues, termed *contextual red flags* are evident in two sources: the medical record and from patients directly.¹⁰ An unexpected increase in glycosylated hemoglobin is an example of the former; a patient's comment that they've recently been having episodes of hypoglycemia reflects the latter. An effective intervention would prompt clinicians to determine whether there are underlying contextual factors that could be addressed in the care plan, averting contextual error. This desirable process is termed *contextual probing*.⁶

While clinical decision support (CDS) has been used to provide physicians with timely biomedical information at the point of care to prevent errors¹¹⁻¹³ and promote appropriate care,¹⁴⁻¹⁶ this technology also affords an opportunity to draw physician attention to both contextual red flags and contextual factors in order to avert contextual errors. The proposed study is submitted in response to Special Emphasis Notice (SEN) NOT-HS-16-015, "Advancing the Collection and Use of Patient-Reported Outcomes and Patient Contextual Data to Improve Quality and Outcomes in Ambulatory Care through Health Information Technology." We will assess the potential of "contextualized CDS" to improve contextualization of care through a randomized controlled intervention trial, with assessment measures of both patient health care outcomes and averted costs associated with overuse and misuse of medical services. In addition to pursuing the aforementioned aim, the study design will adopt best practices for CDS design. We propose to implement highly personalized, concise, actionable contextual CDS strategies. The proposed study will pursue these aims by testing three hypotheses about contextualized CDS, and adhering to one design principle. The three hypotheses are that CDS:

1. *Reduces contextual error*: CDS tools that inform clinicians of contextual factors and prompt them to explore contextual red flags should result in a reduction in contextual error.
2. *Improve health care outcomes*: Contextualized CDS predicts improved health care outcomes defined as a partial or full resolution of the contextual red flag (e.g. elevated HgB A1c) after the index visit.
3. *Reduces avoidable health care costs*: Contextualized CDS is associated with a reduction in misuse and overuse of inappropriate or unnecessary medical services.

The design principle, referred to as "*Five Right*"¹⁷ is to provide the right information to the right people through the right channels in the right format at the right point in care delivery.

To test the hypotheses, patients who consent to participate will be randomized to usual care or care enhanced with contextualized CDS. Participants will audio record their visits, and the data will be coded using 4C. They will be followed for 4-6 months following the index visit for

assessment of outcomes using an established tracking method.⁶ In addition, USPs presenting with cases containing complicating contextual factors that if overlooked result in overuse and misuse of medical services, will be employed to assess the third hypothesis, and to supplement the data obtained by observing the effects of contextual alerts on the care of real patients for the first hypothesis.

2.0 Background/Scientific Rationale

A *contextual error* occurs when a care plan is inappropriate because of inattention to patient context.¹ Increasing the dosage of a patient's medication to manage deterioration of a chronic condition is a contextual error when the unaddressed underlying etiology is something in the patient's circumstances, such as a change in health insurance coverage, loss of social support or competing responsibilities. Contextual errors are a subtype of medical error as they reflect "...a wrong plan to achieve an aim."³

Our team has spent over a decade characterizing contextual errors (what they are and how to detect them), assessing their prevalence in various practice settings, measuring their impact on health care outcomes and costs, and trying to prevent them.^{8,9} For the latter we have attempted medical education interventions,^{4,18} and performance improvement strategies employing audit & feedback.¹⁹ A common theme of all of this work has been that contextual errors occur when physicians overlook essential information about patients' circumstances and behaviors when planning their care, with measurably deleterious consequences for both health care outcomes and costs.²⁰ Reducing contextual error rates may require real time strategies, activated during the clinical encounter, that prompt physicians to explore and address patient context in care planning.

In our research employing real patient collected audio we learned that contextual errors are common. In a study in which 601 patients carried concealed audio recorders into their visits across multiple practice sites, we found that contextual red flags were present in 403 of visits (67%), and that contextual factors were revealed in 208, meaning that in 35% of encounters effective care required identifying and addressing a contextual factor.⁴ Physicians were successful about 59% of the time, and responsible for a contextual error in the remaining 41%. In other words, about 14% (0.41 x 35%) of overall care was derailed by a contextual error. When we followed these patients for 9 months, the presenting problem at the time of the index visit was less likely to improve or resolve compared to visits without a contextual error (46% vs 71%; $P= 0.002$).

In our research employing unannounced standardized patients (USPs), actors presenting to clinicians as patients and collecting audio recordings, we documented similar performance problems, with high contextual error rates.⁷ These errors are caused either by inattention to contextual red flags – i.e. not noticing or responding to clues of underlying contextual factors, or not addressing contextual factors in care planning. The cases we developed were designed such that physicians were also challenged to avoid making biomedical errors, e.g. overlooking evidence of gastroesophageal reflux in a patient with asthma presenting with increased symptoms after meals and when recumbent. Before deploying USPs, the cases were iteratively refined until board certified physicians reviewing paper based versions had a low probability of making either a biomedical or contextual error when explicitly informed of the contextual factor.¹⁰ In situ, however, contextual error rates turned out to be both common and more frequent than biomedical errors. In a subsequent analysis we added up the direct service utilization costs of these errors using Medicare cost-based reimbursement data, by tabulating the expenses associated with misuse and overuse of medical services.⁵ Over 400 encounters, biomedical errors contributed a mean cost of \$30 per encounter, and contextual errors \$231 per encounter (Figure 2).

Clinical Decision Support (CDS) provides a set of strategies for both individualizing and timing heightened awareness of patient specific information to inform decision making. CDS integrates patient specific data with a knowledge base and interprets the resulting data with clinical rules and guidelines to provide support to clinicians at various points in the care process.²⁴ CDS can interact with clinicians in a variety of ways, from interactive alerts to passive

visualization that guides decisions without interrupting clinicians. It can be real time, or a message that can come at a more convenient time for non-urgent information.²⁵

To date the knowledge base in CDS systems has been primarily biomedical information, such as laboratory data, pharmaceuticals, diagnosis, patient allergies, age, sex, etc... We propose incorporating contextual information into the CDS knowledge base to allow CDS interventions that help clinicians pick up on contextual red flags and prevent contextual errors. The approach would embrace the “Five Rights” framework already widely adopted in CDS design.¹⁷ CDS interventions must provide the *right information*, to the *right people*, through the *right channels*, in the right *intervention formats*, at the *right points* in workflow.

In the following section, we outline a plan for incorporating and rigorously assessing patient contextual information (contextual red flags and contextual factors) into CDS, and assessing its impact on contextual error rates, health care outcomes and the misuse and overuse of medical services, drawing on methods of measurement developed, validated and extensively employed in our prior research. In addition to measuring the benefits of contextualized CDS, this project will focus on best design practices, such that the contextual information is presented in a manner that is relevant to those who can act on the information and that results in the right action.

3.0 Objectives/Aims

We will assess the potential of “contextualized CDS” to improve contextualization of care through a 27 month randomized controlled intervention trial, with assessment measures of both patient health care outcomes and averted costs associated with overuse and misuse of medical services. In addition to pursuing the aforementioned aim, the study design will adopt best practices for CDS design. We propose to implement highly personalized, concise, actionable contextual CDS strategies. The proposed study will pursue these aims by testing three hypotheses about contextualized CDS, and adhering to one design principle. The three hypotheses are that CDS:

1. *Reduces contextual error*: CDS tools that inform clinicians of contextual factors and prompt them to explore contextual red flags should result in a reduction in contextual error.
2. *Improve health care outcomes*: Contextualized CDS predicts improved health care outcomes defined as a partial or full resolution of the contextual red flag (e.g. elevated HgB A1c) after the index visit.
3. *Reduces avoidable health care costs*: Contextualized CDS is associated with a reduction in misuse and overuse of inappropriate or unnecessary medical services.

4.0 Eligibility

- *Subjects include*:

- 500 adult patients of primary clinics at UIC and Loyola Medical Center (LUMC) (we estimate approaching 1700 patients to recruit 500)
- The clinicians (physicians or nurse practitioners) seeing the 500 patients (at least 20 clinicians and up to 200 clinicians)
- Maximum subjects under this protocol: 2000 patients, 200 clinicians

4.1 Inclusion Criteria

- English-speaking adult patients presenting to outpatient primary care clinics for scheduled appointments who can be contacted in advance of their appointment and the clinicians (physicians or nurse practitioners) seeing

those patients at those visits. [Later amended to include Spanish-speaking adult patients as well].

- Eligible patients and their clinicians are identified from scheduled clinic appointments

4.2 Exclusion Criteria

- Patients with emergent or unscheduled visits or who do not speak English.

4.3 Excluded or Vulnerable Populations

- Patients who do not speak English are excluded because previously developed tools for assessing context and contextualization are only available in English and our 4C coding system has only been applied in English
- Clinician subjects include UIC and LUMC employees.

5.0 Subject Enrollment

- Clinicians: Clinicians will be informed of the study at their standing staff meetings. They'll be told that the purpose of the project is to assess whether enhanced clinical decision support, that provides both passive and actively delivered information provided by patients and extracted from their medication record about life challenges, or "contextual factors" that may be impacting their health care, can improve clinical decision making and health care outcomes and costs. They'll be informed that if they participate data collection will require listening in on the visit and that we will be inviting patients to audio record their visits. They'll also learn that this is a randomized study so that some of the time they'll see contextualized CDS information and other times they won't. They'll learn that they are not a unit of study, and we will be collecting no data about their individual performance. We'll also inform them that a decision not to participate will not impact their employment in any regard as we are a research team not connected to management. Those indicating they would like to participate will be contacted by an RA to complete the informed consent process
- Patients: The proposed protocol is that patients of participating physicians will be contacted about 2 weeks prior to a scheduled appointment to the adult primary care clinic at either of the two sites. Initial contact will be via mail with an opt out for a follow up phone call. If they don't opt out, the research assistant will call them. They will be informed that they are invited to participate in a study to determine whether providing their health care team with additional information in the electronic medical record about challenges or life circumstances they are facing that impact their care could improve the quality of their care, including their health outcomes. They will be informed that if they participate they will be asked and, assisted if needed, with completing a brief questionnaire for their medical record about challenges they are having that might impact their care. They'll also learn that when they arrive for their appointment they will receive a small digital audio record to carry into the visit. They'll be told that it is preferable to conceal the audio in their pocket or bag, but that they can take it out if they like. They'll be informed that their doctor supports the study. We also encourage all patients to turn off the audio recorder at any time if they change their mind about participation. Finally, they'll be informed that a member of the research team will access their record twice: first to note any information about their life situation that may be relevant to their health care now, and then several months later to see if key health care indicators noted at the visit have improved. Finally, they'll be told that their doctor may or may not receive the information they provided, based on random assignment. We have

allocated \$20 to each patient participant and they'll be told that as well. Those who consent to participate will sign the consent document when they arrive for the appointment and are met by the RA. Only individuals who exhibit a full understanding of the protocol, and indicate they are comfortable recording their visit, are eligible to do so.

6.0 Study Design and Procedures

The protocol for the proposed trial is as follows: (a) Patients are contacted by phone approximately two weeks before a scheduled visit and invited to participate in a randomized controlled study of whether augmenting clinician attention to information about their life circumstances can result in higher quality care with better health care outcomes. (b) Among those who consent to participate, prior to randomization, subjects complete a brief questionnaire consisting of seven questions designed to elicit a broad range of contextual red flags, previously developed and validated with funding from another study (appendix). An affirmative response to any item prompts the respondent to then select one or more contextual factors if present. The instrument will be a commercially available portal tethered to the EHR for data transfer. Those who do not have web access will complete the instrument with the assistance of an RA over the phone before their visit or, if necessary, when they report for their appointment. These data upload (for both the intervention and control group) into the electronic medical record as discrete variables. (c) For those randomized to the intervention, these contextual factors along with contextual red flags already stored in the EHR will produce a variety of CDS, both passive and interruptive alerts. For visits by patients in the control group, the CDS system will not operate (d) Just prior to their appointment, in a private area near the waiting room, participants will receive a small encrypted digital audio recorder to conceal in a bag, or eye glass case or other common personal item. (e) As participants exit the visit, they return the audio recorder to an RA who uploads the audio to a secure server.

[figure not shown]

Figure 1: Participant flow diagram for randomized trial of contextualized clinical decision support in real patients.

Note that while patient encounters will be randomized, physicians will not. Participating physicians will provide care both with and without contextualized CDS. Hence there is no specific physician sample size required for this section of the study.

Randomization of unannounced standardized patients:

There are four reasons to employ USPs to assess the impact of an

intervention (contextualized CDS) on overuse and misuse of medical services. First, they are by definition standardized, meaning that physicians in both the control and intervention groups are seeing the “same” patient.³⁰ This experimental approach enables apples-to-apples comparisons (i.e. intrinsic risk adjustment) of clinical decision making, isolating the intervention as the sole changing variable. Second they assess actual performance in practice, rather than just skills.²² The third reason is that USP cases can be designed around ambulatory presentations for which there is evidence based consensus about what constitutes appropriate care.³¹ For instance, there is consensus that ordering radiographic studies on a patient presenting with uncomplicated lower back pain is an overuse of medical services. Similarly, ordering a malignancy work up on patient with weight loss in the setting of caloric deprivation is a misuse of medical services. The fourth reason is that USPs scripts can be customized around the particular CDS features we seek to assess. For instance, if we seek to assess whether alerts designed to inform clinicians when their patients are not adhering to medications in the setting of deteriorating chronic care management (e.g. a diabetic patients with elevated Accucheck readings in their log book) reduce unnecessary consultation of specialists, prescribing of additional medications etc...we will employ USP scripts that simulate such presentations.

For this project, 4 USP scripts with embedded contextual red flags and factors, drawn from our library of such cases will be selected. Their training and deployment will be managed by the UIC Graham Clinical Performance Center, which has extensive prior USP experience.^{7,32} The scripts will be modified and customized to assess the efficacy of the selected CDS innovations such that failure of CDS to prevent inattention to contextual red flags or factors in USP cases would result in a contextual error. Following the development of the 4 scripts, each script will be portrayed at 10 control visits without CDS support and 10 intervention visits with CDS support, divided across the two sites, for a total of 80 USP visits.

	Year 1	Year 2	Year 3	Year 4
Recruitment and Randomization of Real Patients				
Recruit 500 patients across two sites and assist with patient reported data entry (RA)				
Collect and 4C code audio recorded data (Project Manager and RA)				
Collect Outcomes Data based on tracking outcomes of contextual red flags on 120 patients for 6-9 months				
Randomization and Deployment of USPs				
Identify and train 13 USPs (CPC)				
Conduct 80 USP visits				
Analysis				
Data analyses of contextual error rates, outcomes, and costs of overuse and misuse of medical services				

Table 1: Project Timeline

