This analysis is based exclusively on data generated from the real patient visits: 4C coding has been extensively utilized to track the resolution of contextual red flags. We've demonstrated in a research setting that contextualizing care does predict improved health care outcomes as defined by resolution or partial resolution of the presenting contextual red flag at 6-9 months following the index visit (with the range depending on timing of follow up visit or scheduled tests).⁴ We propose to duplicate the methodology in this project, again tracking the status of the contextual red flags of patients seen at the index visit using a blind methodology, comparing those in the intervention group to the control. A detailed description of the process of scoring for outcomes based on contextualization of care is provided in the Content Coding for Contextualization of Care manual, publicly available.²⁷ As noted above, the outcome of interest is the disposition of the original contextual red flag when followed over time. The criteria for a good or poor outcome are prospectively determined, based on the original red flag, to avoid any bias resulting from knowledge of how the encounter gets coded. Determination of outcome is made blind to whether the index visit was coded as contextualized. A good outcome marks an improvement in the patient's condition as reflected in the contextual red flag. A poor outcome indicates no improvement in the contextual red flag.

Hypothesis 3: Contextualized CDS is associated with a reduction in misuse and overuse of medical services.

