This analysis is based exclusively on data generated from the USP visits, in which physicians in the usual care and contextualized CDS groups see sets of "identical" patients for which misuse and overuse of medical services has been pre-defined. Utilizing our previously published methods,⁵ we will adopt the economic perspective of the patient and their third party payer, if any, with a time horizon of the expected consequences of care during the 30 days following the consultation. We consider only the direct consequences of care associated with diagnosis or misdiagnosis. We will not consider downstream costs beyond the initial recommendations from the consultation, and we will not consider societal costs not incurred by the patient or payer, such as lost productivity. We will include only resources related to the immediate diagnostic and therapeutic management at the index visit. Resources are direct medical costs in the case of unnecessary treatment and foregone direct medical costs in the case of under treatment.

Sample size calculations

Real patients (see Figure 5): Assuming, based on our prior research⁴ and data from the audit & feedback program,¹⁹ that contextual red flags with associated factors will be present in 50% of recorded visits, that 30% of patients approached will consent to participate, that physicians unaided will probe 50% of contextual red flags and that physicians unaided will contextualize care in 50% of visits with contextual factors, we propose to power the study for 80% power to detect an absolute increase in probe rate from 50% to 75% with contextualized CDS, and a corresponding increase in contextualization rates from 50% to 75%. Testing hypothesis 1 requires 58 patients with identified contextual factors per group, and therefore at least 145 patients consented and recorded per group. Testing hypothesis 2 requires at least 60 contextualized care plans in the intervention group and 60 non-contextualized care plans in the control group, which we expect to achieve with 80 identified contextual factors in the

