intervention group (requiring 192 recorded visits) and 120 identified contextual factors in the control group (requiring 288 recorded visits). Thus, to test all project hypotheses, we will approach and consent a sufficient number of patients (approximately 1600) to obtain recordings of 480 patients, randomize them to the intervention and control groups on a 2:3 basis (192 intervention, 288 control), and expect to identify contextual factors associated with red flags in 80 intervention and 120 control patients. As the primary care clinics at the participating sites see approximately 5,000 unique patients (UIC) and 25,000 (Loyola) annually, accrual is likely to require no more than 4-6 months.

Sample size (USPs): In our past work with USPs, physician made contextual errors approximately 80% of the time.⁷ Assuming that the contextualized CDS enhances physician attention to red flags and leads them to probe substantially more often (e.g. increasing probe rate from 50% to 75%) and attend to identified information (e.g. increasing plan rate from 50% to 75%), we would expect overall contextual errors to occur no more than 45% of the time, and 28 control and 28 intervention USP visits would provide 80% power to detect such a difference and test hypothesis 1.

In our past work, we found an overall median cost of error of \$194 when cases presented with contextual red flags, based on a median cost of \$231 when contextual errors occurred and a median cost of \$0 when contextual errors did not occur.⁵ Based on bootstrapped simulation from our cost data in that study, 40 control and 40 intervention USP visits provide 83% power to detect the expected cost reduction (a median of \$156) due to reduced contextual errors using a Wilcoxon rank-sum test with a significance level of $p<.05$. Accordingly, we will conduct 40 control and 40 intervention USP visits to provide sufficient power to test both study hypotheses. As the study comprises 4 USP visits (2 control, 2 intervention) per physician, we will recruit 20 physicians for this portion of the study.

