10.0 Data and Safety Monitoring

We believe this study is minimal risk. However, to ensure the safety of research participants and to comply with NIH policies, a DSMB will be formed in early months of the project and given responsibility to review and approve study methods and analysis plan for the research. The DSMB will be organized by [name] and will consist of senior, experienced clinicians and health services researchers. If deemed necessary by the IRB, the Principal Investigators will not be on the Data Safety and Monitoring Committee, thereby ensuring some level of independent review. When necessary, we will bring in experts from outside the project to serve on the committee. The DSMB will review interim data mid-way through the study using a predetermined stopping rule to determine whether the intervention group is being significantly benefitted (or harmed) over the control group and whether early stopping is necessary. In the rare event that an adverse event attributable to the CDS intervention is found, we will contact the patient's provider and document in the chart the potential error that was found.

One mid-trial (half of patients enrolled) comparison of rate of 4-6 month post-visit resolution of visit contextual red flag for intervention vs. control visits using a mixed effects logistic regression model with random effect of clinic/site and fixed effect of trial arm. An effect of trial arm that is significant at the $p<.01$ level in either direction will trigger early stopping of additional recruiting (however, in patients already recruited who have completed the study visit, we will continue to obtain and analyze their 4-6 month post-visit medical records)

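### Table 1's 120 tracked patients do not match the uncapped by-arm follow-up for Hypothesis 2 or the 200 expected patients; if the row governs, about 40% would have no outcome

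*Combined protocol and SAP*

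**What the plan says.** - **Section 6.0, Table 1 (project timeline):** "Collect Outcomes Data based on tracking outcomes of contextual red flags on 120 patients". The row gives the tracking window as 6-9 months. It is the only place that puts a number on the patients whose outcomes are tracked.
- **Section 9.0, Hypothesis 2:** the analysis rests on "tracking the status of the contextual red flags of patients seen at the index visit using a blind methodology". The contrast is by randomized arm: "comparing those in the intervention group to the control". The section names no sub-sample.
- **Section 9.0, sample size calculations:** "Testing hypothesis 2 requires at least 60 contextualized care plans in the intervention group and 60 non-contextualized care plans in the control group". After 2:3 randomization of 480 recorded patients, the investigators "expect to identify contextual factors associated with red flags in 80 intervention and 120 control patients".
- **Section 10.0, interim look:** a "comparison of rate of 4-6 month post-visit resolution of visit contextual red flag for intervention vs. control visits", made when half the patients are enrolled.
- **Sections 1.0 and 8.0:** participants are followed, and presenting red flags are checked in the chart, at 4-6 months. Neither section limits the number.

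**The concern.** Hypothesis 2 and the interim stopping rule both compare red-flag resolution between randomized arms. That comparison is protected by randomization only if outcomes are sought for all randomized patients with a red flag, or for a subset chosen without regard to anything that happened after randomization. A figure of 120 set against 200 expected patients, with no selection rule, leaves open both who is followed and when the choice is made. Any choice made after the visit has been coded is made after randomization.

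Timing matters too. Section 8.0 has the file linking study codes to medical record numbers destroyed once chart outcomes are extracted. Patients left out of that extraction may be impossible to add later.

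**Working it through.** **1. Where 120 may come from.** Section 2.0 reports that the presenting problem improved or resolved in 46% of visits with a contextual error and 71% of visits without one. Take two-sided alpha 0.05 (an assumption, since the plan states a level only for the standardized-patient cost test and the interim look) and 80% power, with pooled variance and no continuity correction:

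n per group = [1.96 × √(2 × 0.585 × 0.415) + 0.842 × √(0.46 × 0.54 + 0.71 × 0.29)]² / 0.25² = 59.8, so 60.

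This reproduces the plan's 60 per group. The expected yields also reproduce: 80 × 0.75 = 60 contextualized intervention plans and 120 × 0.50 = 60 non-contextualized control plans. The total, 60 + 60 = 120, equals the Table 1 figure. That this is the source of the row is an inference.

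**2. Share without an outcome if 120 is a cap** (1 − 120/N):

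| Patients who should be followed | N | Without outcome |
|---|---|---|
| Flag plus factor at the earlier study's 35% of 480 | 168 | 48 (29%) |
| Flag plus factor, the plan's expected count | 200 | 80 (40%) |
| Flag plus factor at the plan's stated 50% of 480 | 240 | 120 (50%) |
| Any red flag at the earlier study's 67% of 480 | 322 | 202 (63%) |

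The last row matters because the Hypothesis 2 outcome is the fate of the red flag, and a red flag can be present without a contextual factor being revealed.

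**3. What selecting the 60 + 60 set would do.** Suppose the decision support had no effect and the earlier association held. Contextualized intervention visits compared with non-contextualized control visits would still show about 71% against 46%. With 60 per group, that difference reaches p < 0.05 about 80% of the time. With no effect, the 80 intervention patients would yield only 80 × 0.50 = 40 contextualized plans. For 40 against 60, the null standard error is √(0.56 × 0.44 × (1/40 + 1/60)) = 0.1013 and the unpooled one is 0.0964. The probability of significance is then Φ[(0.25 − 1.96 × 0.1013)/0.0964] = about 70%. The contrast would mostly measure the link between contextualization and outcome, not the effect of the intervention.

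**4. What full tracking gives.** Apply the plan's contextualization rates (75% and 50%) and the 71%/46% outcome rates to whole arms:

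- Intervention: 0.75 × 0.71 + 0.25 × 0.46 = 64.75%
- Control: 0.50 × 0.71 + 0.50 × 0.46 = 58.5%
- Difference: 6.25 points

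With 80 against 120, the pooled standard error is √(0.61 × 0.39 × (1/80 + 1/120)) = 0.0704 and the unpooled one is 0.0698. Power is Φ[(0.0625 − 1.96 × 0.0704)/0.0698] = about 14%. With 120 tracked, split 48/72 or 60/60, it is about 10%.

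The detectable difference at 80% power, assuming 50% resolution, is 2.80 × √(0.25 × (1/n₁ + 1/n₂)): 26 points for 48/72, 20 for 80/120 and 16 for 129/193. All are well above 6.25.

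**The case against.** The strongest reply is that Table 1 is a timeline and its row has no limiting word. The operative text points the other way. Every patient is told the record will be opened a second time, several months on, to look for improvement (sections 5.0 and 11.1). Section 10.0 says that even after early stopping, chart outcomes will still be obtained for patients already recruited who completed the visit. The row also carries the 6-9 month window that section 9.0 attributes to the earlier research, while sections 1.0, 8.0 and 10.0 use 4-6 months. It may simply not have been updated. The 60 + 60 requirement is worded as a minimum, and against that set the shortfall is zero.

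Most of this stands, and it limits what can be claimed. A reader might infer that at least 40% of the Hypothesis 2 population will go without an outcome. The documents do not support that: the loss is conditional on the timeline row governing, and 40% is not a floor, since the earlier study's 35% rate gives 29%. A reader might also infer that the investigators intend to follow only patients picked by coding result. No section says so, and section 9.0 fixes the good/poor criteria prospectively and determines outcomes blind to how the visit was coded.

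The reply does not remove the conflict. The one number given for follow-up disagrees with the by-arm analysis, and it coincides with a set defined by a different post-randomization result in each arm.

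**Conclusion.** The point holds as an unresolved inconsistency over who enters outcome follow-up, not as an established restriction to 120. If Table 1 governs, about 40% of the expected flag-plus-factor patients would have no outcome, with a range of 29% to 63% depending on the prevalence assumed and on whether all red-flag visits count. If the 120 are the 60 + 60 set, the heavier consequence is selection: the contrast would no longer be the randomized one that section 9.0 describes for Hypothesis 2, and it could be significant with no intervention effect.

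It would also be wrong to infer that full tracking makes Hypothesis 2 adequately powered. It recovers coverage and the randomized comparison, but power for the by-arm contrast moves only from about 10% to about 14%. Those power figures assume two-sided 5%, independent visits, the plan's 50% and 75% contextualization rates, and the earlier study's 46% and 71% outcome rates.

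**What to change.** 1. Reword the Table 1 row so that outcomes are collected for every randomized patient with a contextual red flag at the index visit, in both arms.
2. State in section 9.0 (Hypothesis 2) and section 10.0 (interim comparison) that this same set is analysed by randomized arm.
3. Reconcile the 6-9 month window in Table 1 with the 4-6 months in sections 1.0, 8.0 and 10.0.
4. Restate the Hypothesis 2 power basis for the by-arm contrast. If the 60 + 60 comparison is kept, label it a non-randomized secondary analysis.
5. Complete the extraction for the whole set before the linking file is destroyed.

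The cost is chart review for roughly 50 to 200 more patients (48 to 202 in the table above). They are already enrolled, have been told of the second record access, and would be reviewed by the research assistants already assigned to this work. No new recruitment or procedure is needed for the tracking. Restating power may show that the trial cannot test Hypothesis 2 at its current size, and that is better known before the analysis.
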